Caloric restriction (CR) (reducing caloric intake up to 50% of normal calorie intake per day)⁸ is a common dietary interventional approach for weight management and cardiometabolic health improvement in adolescents and adults with obesity.⁹ However, studies have shown that CR is hard to maintain, and individuals tend to re-gain the weight after the intervention is completed.¹⁰ Time restricted eating (TRE) has been suggested as an alternative to CR.¹¹ TRE, a type of short-term fasting, is defined as periods of no energy (calories) intake followed by periods of ad libitum (as much as desired) energy intake.¹² The fact that TRE does not intentionally limit energy intake, while CR does, could make it more appealing to individuals with respect to adherence, acceptability and efficacy.¹³ TRE has been shown to be an effective strategy in reducing body fat percentage and waist circumference in adolescents and adults with obesity.^{13,14}

Moreover, high-intensity interval training (HIIT), repetitions of a short period of intense activity followed by a low intensity break, has shown to be effective in improving cardiometabolic health (including lipids, blood pressure, and insulin sensitivity) in adults with obesity compared with other traditional exercise.¹⁵ In addition to its benefits on cardiometabolic health, previous studies have suggested that HIIT can be a time-efficient strategy to enhance body composition and cardiopulmonary fitness in adults with obesity.¹⁶

However, it is unknown if TRE or HIIT will produce a greater improvement of cardiometabolic health. Therefore, the goal of this proposed study is to examine the independent and combined effects of a 4-week TRE and HIIT intervention on cardiometabolic biomarkers in adolescents and young adults.

4. Methods

4.1. Provide a detailed description of what participants will be required to do; including any technical terms or procedures.

Participants: A total of 50 adolescents (age 14-17 years old with sex- and race-specific BMI percentile $\geq 85^{\text{th}}$) and young adults with overweight and obesity (age 18 to 30 years old with BMI $\geq 25 \text{ kg/m}^2$) will be recruited for the study. This is a randomized control trial with 50 participants randomly being assigned into 3 groups: TRE intervention (n=20) or HIIT intervention (n=20), and control (n=10). The following below outlines what participants will be asked to do during each lab visit and during the 4-week of intervention.

A) Pre-lab Contacts:

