and reconstructs it into a pressure wave. From this wave, we can estimate blood pressure in this artery and calculate the stiffness (or how elastic the artery is). This measure takes 5-minutes to complete.

C) Randomization:

Upon completion of the Pre-Intervention Lab Visit, participants will be randomly assigned into one of three groups: (a) TRE, (b) HIIT, and (c) Control. The randomization will be done separately for adolescents and young adults [with the exploratory purpose of future analysis on age-specific difference in interventional effects on cardiometabolic health]. Within each group, we anticipate that there will be an equal number of adolescents and young adults.

(a) Time Restricted Eating (TRE) trial:

Participants randomized into the TRE group will be instructed to consume all their calories within a 10-hour period. We will instruct participants that they can choose their time-window (early TRE [7am – 5pm] or late TRE [1pm – 11pm]), but it must remain constant for the duration of the study. Further, we will give no restrictions on the type of foods and/or the quantities individuals can consume. We will ask individuals to maintain their diet for the duration of the study. Participants will be given clear instructions on their diet and how to use the “MyFitnessPal” application. Participants will have their total daily energy requirement calculated using the following formula (Basal metabolic rate [BMR] x activity level) and will be told to eat that amount within their allotted time window. BMR will be calculated when participants have their body composition taken by the InBody. Participants will be told to start their 4-week diet the following day after visit.

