(b) High Intensity Interval Training (HIIT) trial: The 4-week HIIT intervention will use a stationary bicycle performed 3 times/week (a total of 12 sessions over the 4-week), performing at the CRL. All participants will perform a 20-minute HIIT protocol (20 repetitions of 10-seconds work time followed by 50-seconds resting/active recovery for the first two weeks, and 10 repetitions of 20-seconds work time followed by 100-seconds resting/active recovery for the rest of two weeks; targeted 90% HR_{max}) after 5-minute warm-up (10% HR_{max}). The supervisor (PI: [name] and/or Graduate researcher: [name]) will provide encouragement and supervision for exercise adherence. Heart rate (Polar, Polar Electro Oy, Kempele, Finland) and rating of perceived exertion (RPE; detail described in the questionnaire section) will be recorded.

(c) Control group: Participants randomized into the control group will be told to maintain their daily lifestyle and dietary habits for the duration of the four weeks.

D) Post-Intervention Lab Visits:

Following completion of the 4-week intervention, individuals will be asked to come back to undergo same screening/measurements of the Pre-Intervention Lab Visit (SUNY Upstate and Syracuse University visits). An email will be sent to participants on their last day of the intervention with available time and dates for their visit. This will ensure all individuals will be tested with a similar fasting schedule, regardless of what group they were in.

4.2. Describe how you will have sufficient time to conduct and complete the research?

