The reason we are looking at individuals with overweight and obesity exclusively (Inclusion A), is because we are targeting individuals at high risk for cardiometabolic diseases, such as type 2 diabetes and cardiovascular disease with the purpose of disease prevention. The reason for inclusion criteria B-D is those factors have been shown to impact weight, and therefore could be potential confounders. Due to the two required visits to the lab (i.e., pre- and post- intervention), we need participants who are local (Inclusion E). Since we will be measuring body composition with a BIA device, these individuals will not be able to partake (Inclusion F).

7.6. List all study specific the exclusion/ineligibility criteria. The exclusion criteria must parallel the inclusion criteria:

- A) Adolescents (age <14 years old and/or sex- and race-specific BMI percentile <85th) and adults with normal weight or overweight adults (Age >30 years old and/or BMI <25 kg/m²) will be excluded in the study.
- B) Have at least one of the following chronic medical conditions: heart disease, arrhythmias, diabetes, thyroid disease, bleeding disorder, history of pulmonary disease, hypertension, hepatorenal disease, musculoskeletal disorder, neuromuscular/neurological disease, autoimmune disease, cancer, peptic ulcers, anemia, or chronic infection (HIV).
- C) Have taken any of the following medications: heart, pulmonary, thyroid, anti-hyperlipidemic, hypoglycemic, anti- hypertensive, endocrinologic (e.g., thyroid, insulin, etc.), emotional/psychotropic (e.g., Prednisone, Ritalin, Adderall), neuromuscular/neurological, or androgenic medications (anabolic steroids).
- D) Does not live in the greater Syracuse area.
- E) Has a pacemaker.
- F) For females: are not pregnant or lactating.

We will explain details of the health conditions for the participants to make sure they understand each health condition completely. We will also examine their body composition and blood glucose before we determine whether they are qualified to participate in the study. During the study, if participants have concerns regarding their health conditions, they are free to refuse to participate, or to withdraw from the study at any time. If there is concern about their medical safety, we may recommend participants seek medical attention.

Exclusion criteria will be monitored by [name] [name] and [name], when they contact him and communicate about the study procedure via email and/or phone.

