8.4. Will participants be compensated?

- No. (Skip to Section 9)
- Yes. If yes, answer 8.4.1. and 8.4.2. below.

Note: All information regarding compensation must be included in consent/assent documents.

8.4.1. If Yes, specify the method of compensation (e.g. monetary, course credit, gift card, toy, etc.), the amount of compensation, and how the compensation will be awarded (per task, per session, etc.).

Compensation will be given out after each visit via Amazon gift cards.

50 dollars will be given out after completion of visit one (pre-intervention visit).

50 dollars will be given out after participants complete the first two weeks of the intervention (with the exception of control group).

50 dollars will be given out after participants complete the last two weeks of the intervention (with the exception of control group).

50 dollars will be given out after completion of visit two (post-intervention visit).

In total, 200 dollars will be given out for participants who complete the study protocol. Participants in the Control will obtain 100 dollars upon their completion of the visits.

8.4.2. Describe how compensation will be awarded if the participant withdraws after beginning the study. Compensation cannot be contingent upon full participation and must be pro-rated in a manner that recognizes the time and effort of the participant prior to withdrawal. Provide a copy of the pro-rating schedule.

For the intervention group, there will be four time points for participants receiving compensation. The first and last compensation will be for the time and effort of one-time visit (i.e., one-day measurement visit). If participants come to the lab but are not able to complete all tasks or measurements during the visit, they will receive \$10 for their time and effort for the visit. The second and third compensation will require 2 weeks of intervention. Each compensation will be provided based on their time and effort with the pro-rating schedule below.

[HIIT intervention: lab visit] 1st week of intervention: \$8/day; 2nd week of intervention: \$9/day; 3rd week of intervention: \$8/day; 4th week of intervention: \$9/day

[TRE intervention: home-based food track survey] 1st week of intervention: \$3/day; 2nd week of intervention: \$4/day; 3rd week of intervention: \$3/day; 4th week of intervention: \$4/day

For the control group, the compensation will be given based on their one time visit so pro-rating schedule will not be applicable.

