Data collected will contain only participant study ID numbers. Participant names will not appear on any data collection sheets, nor will names be used as part of data acquisition software. Similarly, only participant study IDs will be used for data analysis spreadsheets. A computer located in the CRL that will house data and data spreadsheets are password protected. All spreadsheets containing data will be password protected. [name], [name], [name], [name], [name], and [name] (under the supervision of [name]) will have password access to spreadsheets. All remaining data (software data entry) are de-identified and will only include participant study ID.

Blood samples obtained from the OGTT will be stored at the HPL (-80 freezer) at Syracuse University. The sample will be stored with the participants' study ID numbers in boxes (no identification on the boxes). All the assay/analysis results will be kept at the password-protected database at the lab at Syracuse University. If the participants withdraw from the study, samples that are designed for the repository will be destroyed but all samples and data that were collected up to that point as part of the research study will be retained for data analysis.

11.3. If you will be sharing data between members of the research team and/or with others, describe how data will be transferred (e.g., courier, mail) or transmitted (e.g., file transfer software, file sharing, email). Please provide the names of the members of the research team listed in either Sections 1 or 6 of the protocol application or any other persons outside of the research team with whom you will share data. If transmitted via electronic networks, describe how you will secure the data while in transit. Specify whether the data you will share is identifiable.

Data will be shared with [name], [name], [name], [name], [name], and [name] (under the supervision of [name]) via Syracuse University One Drive. The data will include identifiable information while it is protected with password and will not be shared any other person outside of the research team.

11.4. If you plan to code the data linking to the participant, describe the method in which it will be coded.

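### The only post-baseline visit is triggered by completing the intervention, with no study day or window from randomisation and no stated visit for participants who stop early

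*Protocol*

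**What the plan says.** The design has two measurement occasions. Section 7.5 justifies the residence criterion this way: "Due to the two required visits to the lab (i.e., pre- and post- intervention), we need participants who are local". Allocation is at the end of the first of them, in every arm: "Upon completion of the Pre-Intervention Lab Visit, participants will be randomly assigned into one of three groups" (section 4.1 C).

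The second is defined in section 4.1 D): "Following completion of the 4-week intervention, individuals will be asked to come back to undergo same screening/measurements of the Pre-Intervention Lab Visit". It is arranged by message: "An email will be sent to participants on their last day of the intervention with available time and dates for their visit". Neither sentence gives a study day, a window or a latest date, and the protocol does not say what happens to the visit if a participant stops the regimen part-way.

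On start dates, section 4.1 C)(a) says of TRE: "Participants will be told to start their 4-week diet the following day after visit". HIIT is 12 sessions at three per week, with no start day and no rule for missed sessions. Control is a four-week period with no stated first day.

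Two other places touch on incomplete participation. Section 8.4.2 pro-rates payment for the intervention weeks: "Each compensation will be provided based on their time and effort with the pro-rating schedule below". Section 11.2 says that when a participant withdraws from the study, "all samples and data that were collected up to that point as part of the research study will be retained for data analysis". Section 8.4.1 pays $50 for visit two as an item separate from the two intervention payments.

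**The concern.** In a randomised comparison, outcome measurement should depend on time since randomisation and not on whether the participant kept to the assigned regimen. Here the trigger is something that happens after randomisation, that the regimen itself can influence, and that has no counterpart in the control arm. If staff apply the words literally, a participant who gives up HIIT or the eating window has not completed and may not be called back, or is called on the day they stop and measured too early. A control cannot fail to complete in that sense.

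With one post-baseline visit, a participant who misses it contributes baseline values only. No analysis plan can supply a measurement that was never scheduled, so this belongs in the protocol. What is at stake is whether the contrasts describe everyone randomised or only those who finished, and whether the interval between measurements is the same in the three arms.

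**Working it through.** The protocol states no dropout rate, effect size, standard deviation or power, so it has no figure of its own to reproduce. The main check is a reading of the text; the arithmetic illustrates scale under stated assumptions.

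**1. What the trigger means for an early stopper.** Take a HIIT participant who stops after 5 of 12 sessions. Section 4.1 D) admits three readings:
- (a) The intervention was not completed, so there is no visit.
- (b) The last intervention day is the day they stopped, so the visit comes early.
- (c) The visit falls at the end of four calendar weeks.

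Reading (a) is the most literal for the active arms. Reading (c) is the only one that works for controls. The protocol does not choose between them.

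**2. Interval between measurements.** Count the pre visit (randomisation) as day 0. A four-week period starting on day s ends on day s + 27. With the visit w days later, the interval is s + 27 + w.
- TRE, s = 1 (stated): w = 1, 7, 14 gives 29, 35, 42 days. The earliest is day 29 and there is no upper limit.
- HIIT or control, s = 7 (assumed): w = 1 to 14 gives 35 to 48 days.
- HIIT or control, s = 14 (assumed): w = 1 to 14 gives 42 to 55 days.

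The delays and the later starts are assumptions. The text allows these differences but does not plan them.

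**3. Completers-only estimate.** Suppose a fraction p of an active arm stops and is not measured, completers have mean change d, stoppers have zero change, and control has zero mean change. The effect in all randomised is (1 − p)d, the observed effect is d, and the overstatement is 1/(1 − p) − 1.
- p = 0.10 (2 of 20): 1/0.90 − 1 = 11%.
- p = 0.20 (4 of 20): 1/0.80 − 1 = 25%.

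**4. A different model.** Suppose the fraction p with the highest tendency to stop is lost, with correlation r between that tendency and a poor response. The shift in the arm mean, in SD units, is r·φ(z_p)/(1 − p), where φ is the standard normal density and z_p its p-quantile.
- p = 0.10: 0.195r, so 0.04 to 0.10 SD for r = 0.2 to 0.5.
- p = 0.20: 0.350r, so 0.07 to 0.175 SD.

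The values of r are assumptions.

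**5. Precision.** Arm sizes are 20, 20 and 10 (section 4.1). The detectable difference at 80% power, two-sided 5%, is (1.960 + 0.842)·√(1/n₁ + 1/n₂) SD.
- Active v control, 20 v 10: 1.09 SD. With 20% lost in both arms (16 v 8): 1.21 SD. With 20% lost in the active arm only (16 v 10): 1.13 SD.
- TRE v HIIT, 20 v 20: 0.89 SD. With 20% lost in both arms (16 v 16): 0.99 SD.

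**The case against.** The strongest reply is that silence is being read as a rule. A reader might infer that early stoppers are barred from the second visit. The protocol does not say that. It calls both visits required, pays for visit two separately from the intervention weeks, and gives the visit to controls, for whom completion can only mean that four weeks have passed. Applying that meaning to all arms removes the exclusion. This stands as a reason for caution, but the sensible reading is not the written one, and staff need to know which to apply.

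A reader might also infer from sections 8.4.2 and 11.2 that stopping the regimen is treated as leaving the study. They do not show this. The form itself requires a pro-rating schedule, and section 11.2 concerns withdrawal from the study, where keeping data already collected is ordinary practice. What remains is that the two events are nowhere distinguished.

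A third inference, that the arms run on different clocks, also goes too far. Randomisation follows the pre visit in every arm and the nominal four weeks is shared. Unequal intervals are possible because only TRE has a stated start day.

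Finally, bias towards benefit cannot be assumed. Controls receive $100 against $200 in the active arms, so they might be lost more often; HIIT sessions are supervised, which may limit stopping; and some who stop may have benefited from partial exposure.

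**Conclusion.** The point holds as a defect in how the outcome visit is defined, with moderate confidence. The only post-baseline assessment is tied to completing the intervention, has no day or window from randomisation, and makes no stated provision for early stoppers. On the literal reading the trigger differs between the active and control arms, and the randomised comparison could become one of completers.

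The documents do not establish that anyone will be lost, how many, or in which direction results would move. The 11% and 25% figures depend on zero change in stoppers and on none of them being measured; the selection model gives 0.04 to 0.175 SD over the same 10% to 20% range. Both show scale only. This is a cheap improvement that prevents a loss which could not be repaired later, and it should be made.

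**What to change.** - **Section 4.1 D):** set the post visit at one target day, with a window, counted from randomisation (the pre visit) and identical in all three arms. State that every randomised participant is invited, with the existing visit-two payment, whether or not they continued the intervention, unless they withdraw consent to further measurement.
- **Sections 8.4.2 and 11.2:** distinguish stopping the intervention from withdrawing from the study, so that the rule on retained data applies only to the latter.
- **Section 4.1 C) and D):** reconcile the text on when the four weeks begin in each arm. This review does not propose an intervention start day.

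The cost is a short amendment. The post visit, glucose tolerance test and $50 payment are already planned for all 50 participants. The downsides are the effort of calling back those who stopped and a probably smaller estimated effect. Some invited participants will still not attend, so the change reduces missing outcomes without abolishing them.

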4.5. Will this research be conducted by SU investigators in foreign countries?

No. (Skip to 4.6)
 Yes. An International Research Form must be completed and submitted with this application.
<http://researchintegrity.syr.edu/wp-content/uploads/2016/10/International-Research-Form-2013.doc>

4.6. Will this research involve genetic testing?

No. (Skip to Section 5)
 Yes. A Genetic Research Form must be completed and submitted with this application.
<http://researchintegrity.syr.edu/wp-content/uploads/2016/10/Genetics.doc>

5. Performance Site Information

5.1. Describe how you will have adequate facilities to conduct your research. Please describe where the researchers will conduct the research and data analysis. Will these activities be conducted on campus using campus facilities, classrooms, laboratories, offices, etc.? Will they be conducted off campus at the researcher(s) home/private office, using agency/organization space, in public spaces, etc.? A combination?

The proposed study is being conducted in the homes of the individual participants as well as the Clinical Research lab (CRL) & the Human Performance lab (HPL) located at the Women's Building (Dept. of Exercise Science), and SUNY Upstate (Clinical Research Unit). Both CRL and HPL are dedicated to the research only, i.e., not being used for teaching. Thus, this space will be available for all aspects of the proposed study. Specifically, the CRL (Women's Building #303) has ~550 sq ft devoted to laboratory research for [name] [name]. The CRL is a newly constructed facility for the purpose of human research in obesity, metabolism, type 2 diabetes, and cardiometabolic disease. This lab is divided into two separate rooms as described: 1) Exam room (~200 sq ft) is for physical (body composition by InBody770) and metabolic testing (oral glucose tolerance test) furnished with outpatient bed, phlebotomy chair, sink and TV/video screening, and for the present study questionnaires from participants will be taken in this space; and 2) Specimen processing & data collection room (~350 sq ft) is for the analysis of the metabolic (blood) samples obtained from the project equipped with YSI 2500 Glucose and Lactate analyzer, Luminex MAGPIX analyzer aligned with desktop PC/software, Labconco Biosafety Logic+ Class II biosafety cabinet, refrigerated centrifuge, vortexer, Bead mixing/dissociation, plate shaker, water bath sonicator and other wet lab

supplies. All measurements collected on participants will be taken in the exam room, and all metabolic markers will be analyzed in the specimen processing & data collection room.

The Human Performance Lab (Women's Building #306) is a 900 sq foot research space dedicated to the non-invasive measurement of vascular structure and function (former direction: [name]; currently being managed by [name]). The pre-clinical Markers of CVD measurements will be performed at HPL. The proposed study is being conducted in the Human Performance Lab (HPL). The HPL is a 900 sq foot research space dedicated to the non-invasive measurement of vascular structure and function. The space consists of a separate conference room area for a private consent process, dedicated cardiovascular testing space, and separate cubicles for graduate students. For the purposes of this specific study, the HPL is equipped with 1 Bod Pod, 1 Bioelectrical Impedance Scale, 1 laser stadiometer, 3 digital scales, 8 blood pressure monitors with central hemodynamic capabilities, 2 heart rate monitors (First Beat), a Watt bike for testing exercise capacity, a clinical-caliber high-end ultrasound, and Sphygmocor tonometer machine for the assessment of arterial stiffness and an Angioscan device to measure finger blood vessel reactivity. Moreover, Clinical Research Unit at SUNY Upstate, directed by [name] (scientific consultant of [name]), have been dedicated to the metabolic testing including oral glucose tolerance test with the purpose of research projects related to individuals with type 2 diabetes. The approval letter from SUNY-Upstate Medical University's IRB Office will be submitted once the protocol is approved. Furthermore, the data analysis will be conducted on Syracuse University campus, including [name] ([name]), CRL and HPL in Women's Building using computers and programs provided by the department.

5.2. List all Performance Sites Other than SU (insert additional rows if needed).

(This may apply when a SU investigator collaborates with a non-SU investigator or institution or an agency/organization will provide space to perform the research. Please check all that apply and add additional sites. Each will require a letter of cooperation and/or IRB approval.)

Check all that apply	Name of Performance Site (list all participating sites below)	IRB Approval and/or Letter of Cooperation
	SUNY Upstate Medical University	 Attached  Pending
	*Syracuse City Schools	 Attached  Pending
	*Other, specify site: _____	 Attached  Pending

**The following additional information is required: contact information for the site, if the site has an IRB, and whether the IRB has approved the research, or plans to defer review to SU's IRB:*

[name] (email: [contact])

5.3. Will this research be conducted in a school or is it funded by the US Department of Education?

No (Skip to 5.4)

Yes. If yes, complete the form found at:

<http://researchintegrity.syr.edu/wp-content/uploads/2016/10/Department-of-Education-Schools-Form.doc>

5.4. Is this a multi-center research project in which Syracuse University will function as the coordinating center/lead institution? (A multi-center study is one where different PIs at different institutions are conducting the same study.)

No

Yes. If yes, describe the plans to manage information obtained in multi-site research that may be relevant to the protection of research participants such as: unanticipated problems involving risks to participants or others, interim results, and protocol modifications:

6. Research Qualifications

CITI training is required for the faculty member listed below and all researchers and research staff who have direct contact with participants and/or identifiable human participant data. NOTE: If training is not completed at the time of submission, approval of your application will be delayed.

6.1. List the names and research qualifications of the primary investigator/faculty advisor listed in Section 1 of this application. Briefly describe the qualifications of the person listed including: Professional Experience, Education (earned degrees only), Licensure (when applicable), Research Experience, CITI Human Research Training modules. Please do not copy and paste your resume or C.V. qualifications.

Qualifications should be appropriate to the type of research being conducted and the targeted population/s involved in the research.

